The primary endpoint of the study is the incidence of clinically relevant hypotension, defined by SBP < 90 mm Hg (confirmed by a repeated value < 90 mm Hg) or symptoms of hypotension, up to 6 hours after the end of study drug infusion. Thus hypotension will be assessed by collection of symptoms and blood pressure measurements.

Symptomatic hypotension is defined as the presence of both low SBP and symptoms (eg, lightheadedness, dizziness, etc.) due to low blood pressure.

Blood pressure measurements should be performed with the subject in a semi-recumbent (about a 30° angle) position, whenever possible.

Blood pressure will be measured as indicated in [Table 5.1-2](#) within (± 5 min in the first hour then ± 0.25 (15 min)) of the specified time points. In addition, sites may perform measurements at intervals defined by institutional standard of care for subjects receiving vasodilators, but no less than what is described in [Table 5.1-2](#).

If the study drug dose is modified (decreased, interrupted, resumed or discontinued), the frequency of blood pressure measurements will follow a more intensive schedule for up to 6 hours following the dose modification (see table below). Upon completion of the intensive schedule, measurements can be either resumed per the original schedule, or follow the discontinuation schedule if the drug is permanently discontinued.

Schedule of Blood Pressure Collection Following a Dose Modification

	30 minutes Post	1 hour post	2 hours post	4 hours post	6 hours post
Dose reduction	X	X	X	X	X
Dose interruption	X	X	X	X	
Dose resumption	X	X	X	X	X
Dose discontinuation	X	X	X	X	X

Details for management of low blood pressure are detailed in [section 5.3.1](#)

In addition to assessments of blood pressure, the Investigator will be asked to collect and assess signs and symptoms of low blood pressure.

Efficacy Outcome Measures: Efficacy assessments will include the following:

Patient assessments of dyspnea severity at rest as measured by the 11-point Numerical Rating Scale (NRS) scores at screening and at 0, 6, 12, 24, 48, 72, and 120 hours after the start of study drug infusion.

Patient assessments of dyspnea severity at rest, using the 7-point Likert scale at 6, 12, 24, 48, 72, and 120 hours after the start of study drug infusion.

Patient assessments of global clinical status using the 7-point Likert scale at 6, 12, 24, 48, 72, and 120 hours after the start of study drug infusion.

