Central Laboratory Assessments			See Section 5.3.5.2 for Analytes
Hematology and Serum Chemistry		X	
Hs Troponin T		X	
NT-proBNP, Serum Cystatin C, NGAL		X	
CRP		X	
Urinalysis		X	
Urine creatinine, Na+, and K+		X	
Efficacy Assessments			
Resting Dyspnea measured by the Numerical Rating Scale (NRS) ^a		X	
Other Assessments			
Sensory Motor Survey		X	

^a If subject is receiving supplemental oxygen, perform NRS without removing oxygen

Table 5.1-2: Treatment and In-Hospital Follow-up (CV013011)

Procedure	Hour 0-23 ^a (Post Rand, Day 1)	Hour 24 ± 2	Hour 48 ± 2	Hour 72 ± 2	Hour 96 ± 2	Hour 120 ± 2 or Discharge ^{b c}	Notes (Time is relative to start of dosing)
Randomize Subject	X						Randomization must take place before Hour 0
Administer Study Medication		X					48 hour continuous infusion *Study medication infusion begin promptly after randomization*
Safety Assessments							
Body Weight		X	X	X	X	X	
Vital Signs: Blood Pressure and Heart Rate ^d	X	X	X	X	X	X	Perform Semi-Recumbent (at a 30° angle) Day 1: Hours 0, 0.25 (15 min), 0.5 (30 min), 0.75 (45 min), 1, 1.5, 2, 4, 5* , 6, 8, 9* , 10, 12, 14, 16, 18, 20, 22 Hours: 24, 28, 32, 36, 40, 44 Hours 48, 54, 60, 66 Hour 72 Hour 96 Hour 120 Perform measurements before IV bag change, when possible. Repeats as per Section 5.3.1 Perform also if signs or symptoms of hypotension *Part I (Cohort 1) only
Respiratory Rate	X	X	X	X	X	X	Day 1: Hours 6 and 12
Use of Oxygen Supplementation,	X	X	X	X	X	X	Day 1: Hours 6 and 12

Table 5.1-2: Treatment and In-Hospital Follow-up (CV013011)

Procedure	Hour 0-23 ^a (Post Rand, Day 1)	Hour 24 ± 2	Hour 48 ± 2	Hour 72 ± 2	Hour 96 ± 2	Hour 120 ± 2 or Discharge ^{b c}	Notes (Time is relative to start of dosing)
Oxygen Saturation							
Temperature		X	X	X	X	X	
12-Lead ECG		X	X	X		X	
Telemetry Monitoring	X						Continuous monitoring through Hour 50

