5.3.1 Assessment of Blood Pressure and Symptoms for Hypotension

The primary endpoint of the study is the incidence of clinically relevant hypotension, defined by SBP < 90 mm Hg (confirmed by a repeated value < 90 mm Hg) or symptoms of hypotension, up to 6 hours after the end of study drug infusion. Thus hypotension will be assessed by collection of symptoms and blood pressure measurements.

Symptomatic hypotension is defined as the presence of both low SBP and significant and/or non-resolving symptoms due to low blood pressure (eg, lightheadedness, dizziness, etc.).

Blood pressure measurements should be performed with the subject in a semi-recumbent (about a 30° angle) position, whenever possible.

Blood pressure will be measured as indicated in Table 5.1-2, within (\pm 5 min in the first hour then \pm 0.25 (15 min)) of the specified time points. In addition, sites may perform measurements at intervals defined by institutional standard of care for subjects receiving vasodilators, but no less than what is described in Table 5.1-2.

If the study drug dose is modified (decreased, interrupted, resumed or discontinued) the frequency of blood pressure measurements will follow a more intensive schedule for up to 6 hours following the dose modification (Table 5.3.1-1). Upon completion of the intensive schedule, measurements can be either resumed per the original schedule, or follow the discontinuation schedule if the drug is permanently discontinued.

Table 5.3.1-1: Schedule of Intensive Blood Pressure Collection Following a Dose Modification

	30 minutes post	1 hour post	2 hours Post	4 hours post	6 hours post
Dose reduction	X	X	X	X	X
Dose interruption ^a	X	X	X	X	
Dose resumption ^b	X	X	X	X	X
Dose discontinuation	X	X	X	X	X ^c

^a dose must be resumed within 4 hours of dose interruption. If interruption last beyond 4 hours, dose must be discontinued and discontinuation schedule must be followed.

^b If dose is restarted within 4 hours following interruption, follow schedule for dose resumption

^c After 6 hours, continue collecting blood pressure measurement at a minimum of every 12 hours through hour 72 or follow the local institutional standard of care protocol, whichever is more frequent.

In addition to assessments of blood pressure, the Investigator will be asked to collect and assess signs and symptoms of low blood pressure The details to be captured will include:

- Onset date/time
- Total duration of episode
- Lowest blood pressure during the episode

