- Signs and symptoms associated with low blood pressure (such as confusion, dizziness, fatigue, auditory disturbances (such as tinnitus), lightheadedness, chest pain, visual disturbances, vomiting, syncope, etc)

Events of clinically relevant hypotension will also be recorded as an Adverse Event (see [Section 6](#))

Management of study drug (interruption, discontinuation, re-start) is detailed in [Section 4.5.1](#). Hypotension endpoints are defined in [Section 8.3](#).

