5.4 Efficacy Assessments

5.4.1 Assessments of Worsening Heart Failure

The Investigator will be asked to indicate if a subject has experienced worsening heart failure, to document the signs, and symptoms that led to the assessment of worsening heart failure, and to document the intensification of treatment implemented for worsening heart failure. Assessment is to be done once daily covering the prior 24-hour period as per the scheduled times in [Table 5.1-2](#).

In this trial, worsening heart failure is defined as **new or worsening signs and/or symptoms of heart failure that require:**

- **Intensification of IV therapy** for heart failure (such as initiation, restart or up-titration of IV diuretics, IV nitrates or other IV vasoactive drugs), *and/or*
- Addition of a mechanical support, either:
 - Ventilatory (mechanical ventilation, noninvasive ventilation),
 - Circulatory (Intra-Aortic Balloon Pump (IABP), ventricular assist device) or
 - Use of ultrafiltration, hemofiltration or hemodialysis specifically for the management of WHF

The presence of WHF must be documented by the investigator recording the signs, symptoms, and/or laboratory assessments that led the conclusion that the subject had worsened.

Symptoms of heart failure may include: dyspnea on exertion, dyspnea at rest, orthopnea, paroxysmal nocturnal dyspnea, persistent coughing or wheezing, fatigue, and abdominal discomfort.

Signs of heart failure might include: pulmonary rales, tachypnea and/or oxygen desaturation, increased jugular venous pressure, hepatomegaly, peripheral edema, an increase in body weight, oliguria, and signs of hypo-perfusion such as mental confusion, hypotension, and cool skin

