8 CONVENTIONS

8.1 Safety Data Conventions

Except as noted in [Section 7.6](#), safety data will be handled according to the BMS safety data conventions. This document includes descriptions on how to analyze AE data as well as how to handle partial dates, missing dates, and unknown end dates when analyzing safety data. If onset time of AEs is missing or incomplete, the onset date of AEs will be used to determine if the AEs will be included in the AE summary tables as follows.

- Non-serious AEs will be included in summary tables if the onset date is on or after the start date of study treatment and not later than the date of Hour 120.
- Serious AEs will be included in summary tables if the onset date is on or after the start date of study treatment and not later than the date of Day 32.

Clinically relevant hypotension defined in the primary endpoint consists of two components which are further clarified as follow:

- The component of “SBP < 90 mm Hg (confirmed by a repeated value < 90 mm Hg)” will be identified by a SBP measurement < 90 mm Hg with confirmatory SBP measurement < 90 mm Hg within 30 minutes after the initial qualifying value. If a confirmatory SBP is missing, the initial SBP will be treated as confirmed if no SBP measurement \geq 90 mm Hg within 30 minutes exists. The assessment time of the initial SBP < 90 mm Hg will include time from start of infusion, up to and including 6 hours after end of infusion.

The confirmatory measurement should be within 15 minutes; however, a window of up to 30 minutes will be applied, to determine if a qualifying confirmatory value is obtained.

- The component of “symptoms of hypotension” will be identified by at least one symptom (other than “low blood pressure”) from the CRF page collecting signs and symptoms of low blood pressure with onset time from start of infusion, up to and including 6 hours after end of infusion

This clarification is also applied to the safety endpoints “The incidence of symptomatic hypotension up to 6 hours after the end of study drug infusion, as well as the incidence of SBP < 90 mm Hg (confirmed by a repeated value)”.

Subjects counted in the endpoint “Percentage of subjects with discontinuation due to symptomatic hypotension” are those who have “Hypotension” as the reason for discontinuation and have a symptom (other than “low blood pressure”) from the CRF page collecting signs and symptoms of low blood pressure with onset time on or before the time of dose discontinuation.

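### On its natural reading, SAP 8.1 derives symptomatic hypotension from a CRF symptom with no check on a measured SBP, although the protocol definition also requires low SBP

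*SAP*

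**What the plan says.** The protocol gives the definition twice. In the synopsis, under blood pressure assessment: "Symptomatic hypotension is defined as the presence of both low SBP and symptoms (eg, lightheadedness, dizziness, etc.) due to low blood pressure". In section 5.3.1: "Symptomatic hypotension is defined as the presence of both low SBP and significant and/or non-resolving symptoms due to low blood pressure". Both need two elements, low SBP and symptoms due to low blood pressure. Section 5.3.1 adds a condition on severity or persistence that the synopsis lacks. Neither gives a mm Hg value for low SBP in this definition.

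SAP 8.1 clarifies the primary endpoint, which is met by either of two components. The first is an SBP below 90 mm Hg with a confirmatory reading. The second is at least one symptom, other than the item for low blood pressure itself, "from the CRF page collecting signs and symptoms of low blood pressure with onset time from start of infusion" up to 6 hours after its end. The section then says "This clarification is also applied to the safety endpoints" and names two: symptomatic hypotension and confirmed SBP < 90 mm Hg. SAP 4.2.2 lists symptomatic hypotension as an endpoint, and SAP 7.6.1 analyses it in the same way as the primary endpoint. Neither adds an SBP condition to it.

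**The concern.** A symptom-only rule suits the primary endpoint, which is an either/or composite. It does not suit an endpoint that the protocol defines by low SBP and symptoms together. Carried over as written, the rule counts a broader event under the protocol's name.

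A measured value matters here because some of the symptoms are not specific to low blood pressure. Protocol 5.3.1 lists "Signs and symptoms associated with low blood pressure (such as confusion, dizziness, fatigue, auditory disturbances" among others. Protocol 5.4.1 includes fatigue among heart failure symptoms ("paroxysmal nocturnal dyspnea, persistent coughing or wheezing, fatigue, and abdominal discomfort") and names mental confusion as a sign of hypoperfusion. In acutely decompensated patients an investigator could attribute such an entry to low blood pressure when the reading was not low.

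Symptomatic hypotension is a named safety objective. It is also among the items that Protocol 8.5 and SAP 7.11 call critical when judging 12 µg/kg/min for Part II. A reader of that row will assume that it counts the event the protocol defines.

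**Working it through.** The plan states no figure for symptomatic hypotension, so there is nothing to reproduce. The check is a comparison of texts.

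1. Elements of the definition, side by side:

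| Element | Protocol synopsis | Protocol 5.3.1 | SAP 8.1 symptom component |
|---|---|---|---|
| Symptom | required | required, with a severity or persistence condition | one CRF entry other than the low-blood-pressure item |
| Attribution to low blood pressure | required | required | implied by the CRF page |
| Low SBP | required, no mm Hg value | required, no mm Hg value | not required |
| Link between SBP and symptom | presence of both | presence of both | none |

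2. Mapping. SAP 8.1 clarifies two components and carries them to two endpoints. The natural assignment is the SBP component to the SBP < 90 mm Hg endpoint and the symptom component to symptomatic hypotension. The neighbouring rule in 8.1, for discontinuation due to symptomatic hypotension, has the same form: a CRF symptom plus hypotension as the stated reason, with no SBP value.

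3. Availability of data. Protocol 5.3.1 captures "Lowest blood pressure during the episode". In Protocol Table 5.1-2 the blood pressure schedule carries the note "Perform also if signs or symptoms of hypotension". A reading should therefore normally exist for each symptomatic episode, but the SAP rule does not use it.

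4. What the planned rows show. If the composite is the union of the two components, then subjects with both = (symptom row) + (SBP < 90 row) − (composite). A reader can recover that overlap from the three rows in SAP 7.6.1. It uses confirmed SBP < 90 mm Hg only and has no time link, so a symptom early in the infusion and a low reading a day later would count together. No output described in the SAP tabulates the two in the same episode.

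5. Assumption-only illustration (composite at the Part I planning case of 10% vs 30%; low SBP taken as confirmed < 90 mm Hg; q points of subjects with a symptom only; half of the remainder with both, so both = 0.5 × (composite − q) and SAP row = both + q): q = 0 gives RR 15/5 = 3.0 on either definition; q = 2 in both arms gives 14/4 = 3.5 for both against 16/6 = 2.7 for the SAP row; q = 6 in both arms gives 12/2 = 6.0 against 18/8 = 2.25; q = 0 on placebo and 6 on active gives 12/5 = 2.4 against 18/5 = 3.6. The values of q and the half share are not in the documents. The line shows only that the effect can be nil or can go either way.

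**The case against.** The strongest case against is that low blood pressure is already built into data capture. The rule does not count any symptom. It counts entries on a page devoted to low blood pressure, where Protocol 5.3.1 also collects onset, duration and lowest pressure. Leaving out the low-blood-pressure item may simply separate symptomatic from asymptomatic episodes. Since the protocol sets no mm Hg value for low SBP here, its definition itself leans on the investigator's judgement, and a programmed threshold would be a sponsor's choice added to it. The one-to-one mapping is inferred, because SAP 8.1 never says that a symptom alone suffices. The SAP rests on Revised Protocol 01 (SAP 2.4), and table contents are deferred to a Data Presentation Plan (SAP 9); neither is supplied. For a safety endpoint, a broader rule errs towards counting too much.

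Much of this stands and limits the point. Attribution by the investigator supplies part of the link to low blood pressure, and the CRF might supply the rest. It does not remove the mismatch. Attribution answers whether the symptom was due to low blood pressure; it does not apply the separate low-SBP element. With the low-blood-pressure item excluded, the rule as written is met by a symptom alone. If the sponsor meant both components together, SAP 8.1 neither says so nor links them in time, so the text needs correcting on either reading.

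A reader might go further and infer that the row dilutes the relative risk, or that the Part II dose decision rests on a faulty measure. The documents support neither. They give no rate of symptom entries without low SBP. SAP 7.11 weighs the row with infusion completion, interruptions, clinically relevant hypotension and other safety data, and SAP 7.1 plans no significance testing.

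**Conclusion.** The mismatch is real on the natural reading of SAP 8.1: a qualifying symptom is enough, where the supplied protocol versions require low SBP as well. It is narrow. What is missing is a check on a measured value, not all connection with low blood pressure. The size and direction of any effect on the relative risk are unknown, and there is none if every symptom entry had low SBP. The primary endpoint accepts symptoms alone and is untouched. Confirmed SBP < 90 mm Hg and dose changes for hypotension are reported separately.

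Severity is minor and confidence moderate. The conclusion assumes the one-to-one mapping and assumes that the unseen CRF page does not itself demand a low reading. Whether Revised Protocol 01 carried the same definition cannot be checked. It would be wrong to read this as showing a biased safety result or a flaw in the primary analysis.

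**What to change.** Keep the symptom-only rule in SAP 8.1 for the primary composite. Give symptomatic hypotension its own derivation: a qualifying symptom plus a measured low SBP in the same episode, using the lowest episode pressure already captured. Before unblinding, the sponsor should state the analysis cut-off for low SBP, the window linking the reading to the symptom, and the rule for a missing episode reading. Report the symptom-only count as a separate row labelled symptoms of hypotension. Reconcile the protocol synopsis with section 5.3.1 on whether symptoms must be severe or persistent, and carry the agreed wording into the SAP.

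The cost is SAP wording, those three decisions and one derivation on data already collected. The tables gain one row. The protocol-defined row can have no more events than the symptom-only row and will probably have fewer, with a wider interval for the relative risk.

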8.2 Baseline Measurements

For analyses involving baseline, the baseline value is defined by the last value prior to the start of infusion, unless otherwise noted.

When there is a missing baseline assessment it will not be imputed, thus, subjects are excluded from any changes from baseline analysis for which they have a missing baseline value.

8.3 Hour Ranges for Analysis of Time Points

Subjects do not always adhere strictly to the visit schedule timing in the protocol. The hour ranges for the analyses of dyspnea measured by 11-point NRS and 7-point Likert scale and patient global assessment (PGA) measured by 7-point Likert scale are defined in Table 8.3-1. The hour ranges for the analyses of laboratory ECG are defined in Table 8.3-2 and 8.3-3, respectively. The hour ranges for the analyses of assessments measured at Hour 24, 48, 72, 96, and 120 (including respiratory rate and temperature) are defined in Table 8.3.4.

Table 8.3-1: Hour Ranges for Analyses of Dyspnea Measured by 11-point NRS and 7-point Likert Scale and PGA Measured by 7-point Likert Scale

Nominal Visit	Target Hour	Hour Ranges
Baseline	Pre-dose	Randomization to \leq Hour 0
Hour 6	Start of infusion + 6	\geq Hour 3 to < Hour 9
Hour 12	Start of infusion + 12	\geq Hour 9 to < Hour 18
Hour 24	Start of infusion + 24	\geq Hour 18 to < Hour 36
Hour 48	Start of infusion + 48	\geq Hour 36 to < Hour 60
Hour 72	Start of infusion + 72	\geq Hour 60 to < Hour 96
Hour 120	Start of infusion + 120	\geq Hour 96 to \leq Hour 132

Table 8.3-2: Hour Ranges for Analyses of Laboratory Measurements

Nominal Visit	Target Hour	Hour Ranges
Baseline	Pre-dose	Randomization to \leq Hour 0
Hour 24	Start of infusion + 24	\geq Hour 12 to < Hour 36
Hour 48	Start of infusion + 48	\geq Hour 36 to < Hour 60
Hour 72	Start of infusion + 72	\geq Hour 60 to < Hour 96
Hour 120	Start of infusion + 120	\geq Hour 96 to \leq Hour 132

Table 8.3-3: Hour Ranges for Analyses of ECG

Nominal Visit	Target Hour	Hour Ranges
Baseline	Pre-dose	Randomization to \leq Hour 0
Hour 48	Start of infusion + 48	\geq Hour 24 to < Hour 60
Hour 72	Start of infusion + 72	\geq Hour 60 to < Hour 96
Hour 120	Start of infusion + 120	\geq Hour 96 to \leq Hour 132

Table 8.3-4: Hour Ranges for Analyses of Respiratory Rate and Temperature

Nominal Visit	Target Hour	Hour Ranges
Baseline	Pre-dose	Randomization to \leq Hour 0
Hour 24	Start of infusion + 24	\geq Hour 12 to < Hour 36
Hour 48	Start of infusion + 48	\geq Hour 36 to < Hour 60
Hour 72	Start of infusion + 72	\geq Hour 60 to < Hour 84
Hour 96	Start of infusion + 96	\geq Hour 84 to < Hour 108
Hour 120	Start of infusion + 120	\geq Hour 108 to \leq Hour 132

Vital signs (blood pressure and heart rate) are assessed at Hours 0, 0.5, 1, 2, 4, 5 (for Part I only), 6, 8, 9 (for Part I only), 10, 12, 14, 16, 18, 20, 22, 24, 28, 32, 36, 40, 44, 48, 54, 60, 66, 72, 96, 120, and Day 32. The hour ranges for the analyses of vital signs are defined in the same manner as in Table 8.3-1 to Table 8.3-4. The hour ranges around planned measurement times are based on the midpoint between planned measurement times, for example, Hour Ranges for Hour 24 is \geq Hour 23 to < Hour 26. Hour Ranges for Hour 120 are \geq Hour 108 to \leq Hour 132. The value collected at the Day 32 visit will be used for the Day 32 time regardless of time ranges.

The hour ranges for the analyses of oxygen saturation are defined in the same manner as in Table 8.3-1 for Baseline, Hours 6, 12, 24, 48, and Table 8.3-4 for Hours 72, 96, and 120.

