7.5.2 Secondary Efficacy Analysis

NT-proBNP will be summarized descriptively for all treated subjects by treatment for each time point, as well as change from baseline. Geometric mean and coefficient of variation (%CV) will also be presented for the original values and percent of baseline.

The NRS is an ordinal scale of 0 to 10. A score of 0 represents “I am not breathless at all” and 10 represents “I am the most breathless I can possibly imagine”.

To incorporate the correlations among NRS assessments at different time points and an appropriate representation of effect of baseline assessments, the change from baseline at time point t (Hour 24, 48, and 72) in NRS assessments will be analyzed using a longitudinal repeated measures method. The model will include treatment, region and time as fixed effects and baseline value as covariate. Furthermore, interaction terms of time by treatment, time by region and time by baseline value will be included. An unstructured variance-covariance matrix for the NRS assessments within same subject will be used (Autoregressive structure will be used if the model does not converge with unstructured matrix.). The SAS[®] procedure PROC MIXED will be used.

After obtaining the estimates of mean change from baseline at time point t in NRS assessments, the mean change in AUC within a treatment group or difference in mean change in AUC between treatment groups will be estimated within the framework of the mixed model, using the formula based on the Trapezoidal rule:

$$\Delta AUC = \sum_{i=1}^3 (t_{i+1} - t_i) \frac{y_{t_{i+1}} + y_{t_i}}{2}$$

where y_{t_i} is the estimate of mean change from baseline at target time t_i in a treatment group for estimation of mean change in AUC within treatment group, and for estimation of difference in change in AUC between treatment groups, y_{t_i} is the estimate of mean difference between treatment groups in change from baseline at target time t_i . The variability of ΔAUC will also be estimated

within the framework of the mixed model in SAS using variability from terms used in the ESTIMATE statement.

Missing values for the dyspnea NRS will only be imputed if a NRS cannot be obtained because the subject has died or is physically unable to complete the form. In these cases, a worst score (i.e. 10) imputation will be used for that time point. Missing values for subjects who are discharged prior to Hour 120 will not be imputed.

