7.6.2.9 Oxygen Saturation

Oxygen Saturation will be summarized descriptively for all treated subjects by treatment for each time point as well as change from baseline.

7.7.1 7-Point Likert Scale

Both the percentage of subjects reporting moderate or markedly improved resting dyspnea and percentage of subjects reporting moderate or marked improvement using the patient global assessment on a 7-point Likert scale will be analyzed and presented in the same manner as the primary endpoint at Hours 6, 12, and 24. Missing values for the Likert scale at Hours 6, 12, and 24 will only be imputed, if a score cannot be obtained because the subject has died or is physically unable to complete the form. In these cases, a worst score imputation (i.e. -3) will be used for that time point.

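### The SAP 8.3 baseline window opens at randomization and so misses the planned pre-randomization central-lab and oxygen saturation baselines; it should follow SAP 8.2

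*SAP*

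**What the plan says.** SAP 8.2 is the section on baseline measurements. It says that "the baseline value is defined by the last value prior to the start of infusion, unless otherwise noted", and protocol 8.4 has the same rule. This rule sets no earliest time. SAP 8.2 also does not impute a missing baseline: "subjects are excluded from any changes from baseline analysis for which they have a missing baseline value".

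SAP 8.3 sets hour ranges for assigning records to nominal visits. In all four of its tables (dyspnea and global assessment scales, laboratory, ECG, respiratory rate and temperature) the baseline range is "Randomization to \leq Hour 0". Oxygen saturation is brought in by reference: "The hour ranges for the analyses of oxygen saturation are defined in the same manner as in Table 8.3-1 for Baseline".

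The analyses that use these baselines include:
- NT-proBNP, summarized as change from baseline, with geometric means that "will also be presented for the original values and percent of baseline" (SAP 7.5.2);
- troponin T and the other laboratory changes (SAP 7.6.2.4);
- oxygen saturation, summarized "by treatment for each time point as well as change from baseline" (SAP 7.6.2.9).

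On timing, protocol Table 5.1-2 states: "Randomization must take place before Hour 0". Table 5.1-1 marks the central-lab row "NT-proBNP, Serum Cystatin C, NGAL" in its pre-randomization column.

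**The concern.** The 8.3 window is the gap between randomization and the start of infusion, which the protocol wants kept short. Samples taken just before randomization fall outside it. Because 8.2 allows exceptions, a programmer could reasonably take the assessment-specific rows in 8.3 as that exception. The planned baseline sample would then be discarded, the baseline would be missing, and 8.2 would remove the subject from the change analysis.

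A secondary endpoint (NT-proBNP change) and a named safety endpoint (troponin T change) are at stake. Subjects who stayed in would be those with a delayed or repeated draw, a selected subset whose representativeness cannot be judged. The sponsor also sees unblinded Part I data at the first interim analysis (SAP 2.3), so a baseline rule settled only during later programming would not be prespecified.

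**Working it through.** The plan gives no figure to reproduce. The check lays the scheduled times in protocol Tables 5.1-1 and 5.1-2 over the window from randomization to Hour 0. The placements below are the same in Revised Protocols 02 and 02c.

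| Assessment (SAP table) | Pre-dose mark | Next mark | Scheduled inside the window |
|---|---|---|---|
| Central labs, six rows (8.3-2) | Pre-randomization, 6 of 6 | Hour 24 (four rows), Hour 48 (CRP), Hour 72 (urinalysis) | 0 of 6 |
| Oxygen saturation (8.3-1 by reference) | Screening and pre-randomization | Hour 6 | 0 |
| Dyspnea NRS (8.3-1) | Pre-randomization in the tables; the synopsis lists Hour 0 | Hour 6 | 0 by the tables, 1 by the synopsis |
| 12-lead ECG (8.3-3) | Screening; that column runs up to 0 hours | Hour 24 | Cannot be determined |
| Respiratory rate (8.3-4) | Screening and pre-randomization | Hour 6 | 0 |
| Temperature (8.3-4) | Screening and within 15 minutes before randomization | Hour 24 | 0 |
| Blood pressure, heart rate | Screening, pre-randomization and Hour 0 | 15 or 30 minutes, by version | 1 |

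The six central-lab rows are hematology and chemistry; hs-troponin T; NT-proBNP with cystatin C and NGAL; CRP; urinalysis; and urine creatinine, sodium and potassium.

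Take a subject whose central NT-proBNP sample is drawn before randomization and who has no further draw before infusion.
- Under 8.2, that sample is the latest pre-infusion value. It is the baseline, and the subject is analyzed.
- Under Table 8.3-2 read literally, the sample precedes the window. There is no baseline, and 8.2 excludes the subject.

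Subjects lost under 8.2: none. Subjects lost under the literal reading: everyone with no value between randomization and Hour 0. The documents do not say how many that would be, so the possible range runs from none to all of about 100 subjects in Part I and about 210 in Part II.

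Two other provisions were checked as possible remedies. SAP 8.4 does not help, because it only chooses among records already in the same window or visit. Local screening results are not a safe substitute: they too would usually precede randomization, and protocol 5.3.5.1 lets the local test be BNP instead of NT-proBNP, or another troponin assay.

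**The case against.** The best defence is that the documents point to one sensible reading. SAP 8.2 is the baseline section, 8.3 exists only to handle departures from the visit schedule, and its baseline target is simply pre-dose. Protocol 8.4 repeats the 8.2 rule, and protocol 6.6 calls the pre-randomization liver tests baseline. A reading that removes most baselines for an endpoint the SAP defines as a change cannot be what was meant. This stands as evidence of intent and lowers the severity. It does not correct the rows, which as written exclude the planned samples.

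Several limits on scope also stand:
- The SAP follows Revised Protocol 01 (SAP 2.4), whose schedule is not supplied. Its lettering of some inclusion criteria in SAP 7.2 differs from both supplied versions.
- The central-lab rows carry no clock time, and telemetry in the same column is timed to the infusion. Some draws could fall after randomization.
- The screening ECG may or may not fall in the window.
- The SAP specifies no explicit change-from-baseline analysis for respiratory rate or temperature, so no consequence is shown for them.
- SAP 8.1 refers safety data to a sponsor conventions document that is not supplied and might address baseline. That would not reach NT-proBNP, which is an efficacy endpoint.

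A reader might infer that 8.2 and 8.3 flatly contradict each other, or that the NT-proBNP and troponin T summaries would certainly be empty. The documents support neither. The exception clause in 8.2 leaves room for both sections, and late or repeat draws could leave some subjects in.

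**Conclusion.** The point holds as a wording error that should be fixed. The SAP 8.3 baseline rows do not fit SAP 8.2 or protocol 8.4. In the supplied schedules they exclude the planned baselines for all six central-lab rows and for oxygen saturation. Followed literally, they would drop subjects sampled before randomization from the NT-proBNP, troponin T and other central-lab change summaries and from the oxygen saturation change. Under 8.2, probably the intended rule, nobody is lost. Whether the NRS is touched depends on whether sites followed the schedule tables or the synopsis.

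The primary hypotension endpoint uses no baseline, and blood pressure and heart rate have a scheduled Hour 0 reading, so these are unaffected. Summaries by time point that use no baseline are also unaffected. Confidence is medium. The conclusion assumes that the Revised Protocol 01 schedule placed these samples as the supplied versions do, and that samples in the pre-randomization column were mostly drawn before randomization.

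**What to change.** In Tables 8.3-1 to 8.3-4, replace the baseline range with: *per Section 8.2, the latest value before infusion starts, including screening and pre-randomization values*. Oxygen saturation then follows through its reference to Table 8.3-1.

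Add one sentence: *for central-lab analytes, baseline is the last central-lab value before infusion; local screening results are not substituted*. This is needed even under 8.2, which does not separate central from local results. Defining it as the last central value, and not as the pre-randomization sample, also covers a central draw taken after randomization.

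The cost is one line in each of four tables plus one sentence, with no new data. The NRS mismatch between the synopsis (Hour 0) and the schedule tables (pre-randomization) is a separate protocol wording point, and this change does not depend on it.
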